#### **Supplementary analyses**

We will conduct preplanned supplementary analyses to assess possible effect modification by other vaccines given during follow-up, previous BCG vaccination, and COVID-19 vaccination before inclusion. These will be done using the same methods as described above for the primary (composite) outcome and for all secondary outcomes.

1. Before and after receipt of subsequent vaccines, and adjusted by type of subsequent vaccine, to assess possible interaction between BCG and other vaccines. Vaccination status will be categorized as 1) No other vaccines, 2) COVID 19 vaccine, 3) Influenza vaccine, or 4) COVID 19 and influenza vaccine.

Vaccination status will be included as a time varying covariate changing on the date of vaccination with subsequent vaccines received during follow-up. Some participants received a pneumococcal vaccine (23-valent polysaccharide vaccine) together with their influenza vaccine as was recommended by the Danish Board of Health in 2020. We will therefore include influenza vaccines with or without concurrent pneumococcal vaccination (given on the same day). Participants will be censored upon receipt of any other vaccines than the above mentioned.

2. By previous BCG vaccination (Yes/no, self-reported and assessed by BCG scar) to assess the effect of revaccination vs. first vaccination with BCG.

3. By COVID-19 vaccination status at inclusion (Received COVID 19 vaccines yes/no).

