### **Sample size**

With an expected incidence of “acute infection” of 20% we will be able to show a 25% reduction in the risk of acute infection in the intervention group compared to the placebo group by including a total of 1890 individuals: 945 individuals in each group. Since the primary outcome data to a large extent are obtained via national registers, we anticipate limited loss of power due to loss to follow-up. We therefore aimed to enroll 1900 participants.

Due to the pandemic and varying infectious disease precautions, recruitment took longer than anticipated, and we ended up recruiting a total of 1706 participants (90% of the anticipated sample size) between September 2020 and December 2021.

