## **4.0 STATISTICAL PRINCIPLES**

### **Levels of confidence and p-values**

A double-sided p-value of  $< 0.05$  will be considered statistically significant. 95% confidence intervals will be provided.

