### Exploratory analysis

Participants were enrolled during different stages of the COVID-19 pandemic. We will therefore conduct a subgroup analysis of all outcomes comparing participants included in the same phase of the pandemic. We will compare outcomes for participants included in the following periods:

1. September 2020 to January 2021 (N=1239); before the COVID-19 vaccines were widely distributed to the target population. A period characterized by increasing infection control measurements and concluding in lockdown.
2. April to December 2021 (N=438); Participants are now being vaccinated with the new coronavirus vaccines; most have had the two or three doses before enrollment. A period characterized by varying COVID-19 activity; a minimum of restrictions on society despite periodically high transmission rates (Omicron variant in the fall).

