**Table 2 Results primary and secondary outcomes**

Outcome	Number (%)		Hazard ratio (95% CI)	Absolute risk reduction (95% CI)
	BCG N=xxx	Placebo N=xxx		
Primary outcome				
Acute infection	xx (x.x)	xx (x.x)	x.xx (x.xx–x.xx)	x.x% (x.x%–x.x%)
Death	xx (x.x)	xx (x.x)	x.xx (x.xx–x.xx)	x.x% (x.x%–x.x%)
Hospitalization	xx (x.x)	xx (x.x)	x.xx (x.xx–x.xx)	x.x% (x.x%–x.x%)
Antibiotics	xx (x.x)	xx (x.x)	x.xx (x.xx–x.xx)	x.x% (x.x%–x.x%)
Doctor	xx (x.x)	xx (x.x)	x.xx (x.xx–x.xx)	x.x% (x.x%–x.x%)
Secondary outcomes				
Self-reported respiratory infection	xx (x.x)	xx (x.x)	x.xx (x.xx–x.xx)	x.x% (x.x%–x.x%)
Verified COVID-19	xx (x.x)	xx (x.x)	x.xx (x.xx–x.xx)	x.x% (x.x%–x.x%)
All-cause hospitalization	xx (x.x)	xx (x.x)	x.xx (x.xx–x.xx)	x.x% (x.x%–x.x%)

**Table 3 Supplementary analyses to explore possible effect modification by sex, age group, other vaccines, previous BCG, and COVID-19 vaccination status at inclusion.**

	Number (%)		Hazard ratio (95% CI)	Absolute risk reduction (95% CI)
	BCG N=xxx	Placebo N=xxx		
Acute infection – also where numbers permit subdivided on each of the outcomes included in the composite outcome.				
Females	xx (x.x)	xx (x.x)	x.xx (x.xx–x.xx)	x.x% (x.x%–x.x%)
Males	xx (x.x)	xx (x.x)	x.xx (x.xx–x.xx)	x.x% (x.x%–x.x%)
Age < 75	xx (x.x)	xx (x.x)	x.xx (x.xx–x.xx)	x.x% (x.x%–x.x%)
Age ≥ 75	xx (x.x)	xx (x.x)	x.xx (x.xx–x.xx)	x.x% (x.x%–x.x%)
Other vaccines received after randomization:				
Effect of intervention before other vaccines	xx (x.x)	xx (x.x)	x.xx (x.xx–x.xx)	x.x% (x.x%–x.x%)
Effect of intervention after other vaccines	xx (x.x)	xx (x.x)	x.xx (x.xx–x.xx)	x.x% (x.x%–x.x%)
Effect after other vaccines, by type of vaccine received:				
COVID vaccine	xx (x.x)	xx (x.x)	x.xx (x.xx–x.xx)	x.x% (x.x%–x.x%)
Influenza vaccine	xx (x.x)	xx (x.x)	x.xx (x.xx–x.xx)	x.x% (x.x%–x.x%)
Both vaccines	xx (x.x)	xx (x.x)	x.xx (x.xx–x.xx)	x.x% (x.x%–x.x%)
Has BCG scar 	xx (x.x)	xx (x.x)	x.xx (x.xx–x.xx)	x.x% (x.x%–x.x%)
No BCG scar 	xx (x.x)	xx (x.x)	x.xx (x.xx–x.xx)	x.x% (x.x%–x.x%)
CoV vaccinated before enrollment:				
Yes	xx (x.x)	xx (x.x)	x.xx (x.xx–x.xx)	x.x% (x.x%–x.x%)
No	xx (x.x)	xx (x.x)	x.xx (x.xx–x.xx)	x.x% (x.x%–x.x%)
Included period 1 	xx (x.x)	xx (x.x)	x.xx (x.xx–x.xx)	x.x% (x.x%–x.x%)
Included period 2 	xx (x.x)	xx (x.x)	x.xx (x.xx–x.xx)	x.x% (x.x%–x.x%)

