### **Sample size**

We aim to include 75 participants in each group, 300 in total. With an anticipated seroconversion rate of 50% in the control group, we should be able to show a 30% increase in seroconversion rate associated with BCG vaccine with 80% power and an alpha of 0.05, anticipating 10% loss to follow-up.

All participants are followed for clinical symptoms for six months. With this sample size, we will only be able to show differences in clinical symptoms if such differences are pronounced.

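### Part A sets out to assess effect modification but specifies no treatment-by-modifier term, and Table 3 has no place for an interaction estimate

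*SAP*

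**What the plan says.** Section 7.0 of Part A, under Supplementary analyses, states the aim: "to assess possible effect modification by other vaccines given during follow-up, previous BCG vaccination, and COVID-19 vaccination before inclusion". The method is that of the main analyses, meaning Andersen-Gill or standard Cox models that give a treatment hazard ratio with 95% CI. Item 1 there speaks of interaction between BCG and later vaccines. It enters a four-level vaccination status as a time-varying covariate, but words this as adjustment by type of vaccine.

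The Methods paragraph of the same section adds analyses stratified by sex and age group, and applies clustering on couples to the non-stratified analysis. The Exploratory analysis paragraph adds inclusion period: "We will compare outcomes for participants included in the following periods".

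Table 3 (section 8.0) is titled as serving "to explore possible effect modification by sex, age group, other vaccines, previous BCG, and COVID-19 vaccination status at inclusion". Its columns are number (%), hazard ratio (95% CI) and absolute risk reduction (95% CI), one line per stratum. The only decision rule in Part A is in section 4.0: "A double-sided p-value of $< 0.05$ will be considered statistically significant".

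**The concern.** Effect modification is a statement about the difference between stratum effects, and on the hazard scale its measure is the ratio of hazard ratios. Neither the text nor the shell table contains that ratio, its confidence interval or a test of it. What remains is a long list of stratum hazard ratios and a 0.05 threshold. This invites the reading that BCG works in one sex, age group or vaccination state and not in another because one interval excludes 1 and the other does not. That comparison is not a test of a difference, and it goes wrong often when the effect is uniform.

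**Working it through.** **1. Count of Table 3.** Rows per outcome: sex 2, age 2, before/after other vaccines 2, type of later vaccine 3, BCG scar 2, COVID-19 vaccination before enrolment 2, inclusion period 2. Total 15.

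- 15 × 4 outcomes = 60 hazard ratios.
- Modifiers named under Supplementary analyses: (2 + 3 + 2 + 2) × 4 = 36.
- Sex and age: 4 × 4 = 16. Inclusion period: 2 × 4 = 8.
- The composite's four components, to be shown where numbers permit, could add up to 4 × 15 = 60 more.

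**2. The plan's own sample size.** The SAP says "we will be able to show a 25% reduction in the risk of acute infection" "by including a total of 1890 individuals: 945 individuals in each group", from an expected incidence of 20% (so 15% under BCG). Part A states no power; Part B states "with 80% power and an alpha of 0.05". Assuming 80% for Part A too:

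- n = [1.96·√(2·0.175·0.825) + 0.8416·√(0.16 + 0.1275)]² / 0.05² = 906 per arm.
- With continuity correction: 945 per arm, 1890 in total. The stated figure is reproduced.

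**3. Assumed events.** The SAP gives no event count. With 1706 recruited (853 per arm) and the planned risks, first events = 853 × 0.20 + 853 × 0.15 ≈ 299, or 1706 × 0.20 ≈ 341 with no effect. The primary analysis counts recurrent events, so these are rough stand-ins, and I also use 100 and 600.

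**4. Same effect in both strata: how often is exactly one significant?** In a stratum with e events, SE(log HR) ≈ 2/√e. With HR = 0.75, log HR = −0.288. Stratum power p ≈ Φ(0.288/SE − 1.96), and P(exactly one) = p₁(1 − p₂) + p₂(1 − p₁).

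| Total events | Split | Stratum SE | Exactly one significant |
|---|---|---|---|
| 100 | equal | 0.283 | 29% |
| 299 | equal | 0.164 | 49% |
| 600 | equal | 0.115 | 42% |
| 299 | 74:26 (1239 and 438) | 0.135 and 0.226 | 53% |

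For equal strata the value cannot exceed 50%, which is reached when stratum power is 50%. An interaction test at two-sided 0.05 is falsely positive in 5% in every row.

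**5. A check that does not use stratum significance.** For two equal strata with the same true effect, the SE of the difference in log HR is √2 times the stratum SE. The chance that the two hazard ratios differ at least 1.25-fold is 2Φ(−0.223/SE_diff): 58% at 100 events, 33% at 299 and 17% at 600.

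**6. What an interaction test can detect.** The ratio of hazard ratios with 80% power is exp(2.80·SE_diff), where SE_diff = 2√(1/e₁ + 1/e₂).

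- Equal strata: 1.91 at 299 events, 1.83 at 341.
- 74:26 split: 2.09 at 299 events, 2.00 at 341.
- Equal strata at the ends of the range: SE_diff = 0.400 gives about 3.1 at 100 events; 0.163 gives about 1.6 at 600.

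**7. Number of interaction tests.** Six modifiers (sex, age group, later-vaccine status as one three-term test, previous BCG by scar, COVID-19 vaccination at inclusion, inclusion period) × 4 outcomes = 24. At 5% each, 1.2 false positives are expected. If independent, P(at least one) = 1 − 0.95²⁴ = 71%.

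**The case against.** The strongest reply is that item 1 names interaction and uses a time-varying vaccination status, from which separate before and after effects would naturally come through product terms. That is a fair reading of intent for this one modifier, so it would be too strong to say that no interaction model is meant anywhere. But the text says adjustment, and a main-effect adjustment gives one common BCG hazard ratio. No product term is written, and Table 3 could not show it. The other modifiers have no such wording.

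A reader might also infer that the authors can only conclude by asking which strata are significant, and so will report a benefit in one group and none in another. The SAP does not support that. It states no such rule, Table 3 shows intervals rather than p-values, and for disjoint strata an approximate ratio of hazard ratios can be worked out from them. This helps less than it seems. The before and after rows share participants, the vaccine-type rows are nested in the after row, and couples can be divided across sex or age strata while clustering is promised only for the non-stratified analysis.

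It is tempting, too, to stress that 60 hazard ratios at 5% give 3 false positives on average if BCG does nothing. The arithmetic is right, but many rows overlap, the SAP presents the table as exploring modification, and interaction tests leave about 24 comparisons. Multiplicity is a matter of labelling and is not the main point.

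Finally, the inclusion-period analysis is already headed exploratory, can be read as a BCG-placebo comparison within each phase, and is not among the modifiers in Table 3's title. The 53% is therefore only an illustration of an unequal split.

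**Conclusion.** The point holds as a mismatch between aim and method: Part A asks about effect modification and specifies neither the term nor the table entry that would measure it. Under the assumed hazard ratio of 0.75 in two equal strata, apparent disagreement in significance arises in roughly 30% to 50% of trials over 100 to 600 events, against 5% for an interaction test. These figures rest on assumed event counts, a normal approximation and first events standing in for a recurrent-event analysis. They show what stratum results can do by chance; they do not predict what the authors will claim. The primary estimate and the sample size are unaffected. The analyses are supplementary or exploratory, so this is a change that should be made rather than a flaw in the main result.

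**What to change.** For each modifier, specify one model with treatment, modifier and their interaction, using couple-clustered standard errors. The four-level time-varying vaccination status needs three interaction terms and one joint test. Add to Table 3 the ratio of hazard ratios with 95% CI and the interaction p-value. State that conclusions on effect modification rest on these and not on stratum significance. Label the roughly 24 tests exploratory and unadjusted for multiplicity.

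No new data are needed; the cost is a few model terms and extra table columns. The real downside is precision: with 299 to 341 events, only a ratio of hazard ratios of about 1.8 to 2.1 has 80% power. A non-significant interaction must therefore not be reported as proof of a uniform effect, and its interval will show how little the strata can distinguish.

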## 6.0 DESCRIPTION OF OUTCOMES AND VARIABLES

### Primary outcome

The primary outcome is a composite outcome: acute infection identified either by a doctor, by antibiotics use, by hospitalization, or by death due to infection. All subcomponents will also be presented separately.

Information on hospitalizations, deaths, and antibiotics use is retrieved from national health registers: The Danish National Patient Register, The Central Person Register, and The National Prescription Register. All hospital contacts due to acute infection will be included, regardless of duration of the contact. An acute infection event identified by a doctor is defined as newly onset infectious illness that has prompted the participant to seek medical attention from general practitioner (GP) or on-call doctor and is based on self-reporting. Participants are asked in the questionnaires, if they have needed to see their GP or an on-call doctor due to newly onset illness during the past 14 days (yes/no). Thus, participants can only have one such event per survey period (14 days). For all outcomes, a honeymoon period of 14 days will be used to define new events.

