#### Primary outcome:

Acute infection will be analyzed as a recurrent time-to-event using an Andersen-Gill Cox proportional hazards regression model with time since inclusion as underlying time scale.

The proportional hazards assumption will be tested using Schoenfeld residuals. The analysis

will be done for the composite outcome and for all the subcomponents separately presenting hazard ratio with 95% confidence intervals for each. Absolute risk reductions will be calculated using Cox regression.

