#### **Secondary outcomes:**

The secondary endpoint self-reported respiratory infection will be analyzed the same way as the primary endpoint. As participants are only able to report one infectious episode during a follow-up questionnaire, the event will be assigned to the first day within the questionnaire period, and the following 14 days of follow-up excluded for analyses as it represents risk free time.

The secondary outcomes verified SARS-CoV-2 infection and all-cause hospitalization will be analyzed in a standard Cox proportional hazards model, but otherwise as described above.

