**Self-reported respiratory infection**

Females	xx (x.x)	xx (x.x)	x.xx (x.xx–x.xx)	x.x% (x.x%–x.x%)
Males	xx (x.x)	xx (x.x)	x.xx (x.xx–x.xx)	x.x% (x.x%–x.x%)
Age < 75	xx (x.x)	xx (x.x)	x.xx (x.xx–x.xx)	x.x% (x.x%–x.x%)
Age ≥ 75	xx (x.x)	xx (x.x)	x.xx (x.xx–x.xx)	x.x% (x.x%–x.x%)
Other vaccines received after randomization:				
Effect of intervention before other vaccines	xx (x.x)	xx (x.x)	x.xx (x.xx–x.xx)	x.x% (x.x%–x.x%)
Effect of intervention after other vaccines	xx (x.x)	xx (x.x)	x.xx (x.xx–x.xx)	x.x% (x.x%–x.x%)
Effect after other vaccines, by type of vaccine received:				
COVID vaccine	xx (x.x)	xx (x.x)	x.xx (x.xx–x.xx)	x.x% (x.x%–x.x%)
Influenza vaccine	xx (x.x)	xx (x.x)	x.xx (x.xx–x.xx)	x.x% (x.x%–x.x%)
Both vaccines	xx (x.x)	xx (x.x)	x.xx (x.xx–x.xx)	x.x% (x.x%–x.x%)
Has BCG scar 	xx (x.x)	xx (x.x)	x.xx (x.xx–x.xx)	x.x% (x.x%–x.x%)
No BCG scar 	xx (x.x)	xx (x.x)	x.xx (x.xx–x.xx)	x.x% (x.x%–x.x%)
CoV vaccinated before enrollment:				
Yes	xx (x.x)	xx (x.x)	x.xx (x.xx–x.xx)	x.x% (x.x%–x.x%)
No	xx (x.x)	xx (x.x)	x.xx (x.xx–x.xx)	x.x% (x.x%–x.x%)
Included period 1 	xx (x.x)	xx (x.x)	x.xx (x.xx–x.xx)	x.x% (x.x%–x.x%)
Included period 2 	xx (x.x)	xx (x.x)	x.xx (x.xx–x.xx)	x.x% (x.x%–x.x%)

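### In Part A supplementary analysis 1, self-reported respiratory infections are dated to the start of the 14-day window but vaccination status to the exact day, so some post-vaccination infections count under the earlier status

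*SAP*

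**What the plan says.** Three parts of SAP Part A bear on this.

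- **Event date.** Section 7.0, Secondary outcomes, says of self-reported respiratory infection that "the event will be assigned to the first day within the questionnaire period", with "the following 14 days of follow-up excluded for analyses as it represents risk free time". Section 6.0 puts the survey period at 14 days. The model is the one used for the primary outcome, an "Andersen-Gill Cox proportional hazards regression model with time since inclusion as underlying time scale".
- **Vaccination date.** Section 7.0, Supplementary analyses, item 1, splits follow-up by later vaccination: "Vaccination status will be categorized as 1) No other vaccines, 2) COVID 19 vaccine, 3) Influenza vaccine, or 4) COVID 19 and influenza vaccine". The status is time-varying: "Vaccination status will be included as a time varying covariate changing on the date of vaccination with subsequent vaccines received during follow-up".
- **Scope.** The same section states: "These will be done using the same methods as described above for the primary (composite) outcome and for all secondary outcomes". Self-reported respiratory infection is a secondary outcome, so it keeps its window-start dating in this analysis. Table 3 in section 8.0 has a row for it labelled "Effect of intervention before other vaccines", followed by rows for after other vaccines and by vaccine type.

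The SAP has no rule that reconciles the two dates. It does not use an onset date, define status per window, exclude the window of vaccination, or plan a sensitivity analysis.

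**The concern.** The event date can only be moved earlier than true onset, never later, while the vaccination date stays where it is. Take a window covering days 28 to 41, a first other vaccine on day 31 and a cold starting on day 38. The cold is dated day 28 and counted as occurring with no other vaccines, a week after the vaccine was given. The opposite error cannot occur, so the errors do not cancel.

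The analysis is there to show whether BCG interacts with other vaccines. Moving post-vaccination infections into the *before* row mixes some of the *after* effect into it. That shrinks the contrast being sought and shifts the event counts that Table 3 prints. A finding of no interaction for this outcome becomes slightly harder to interpret.

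**Working it through.** The SAP gives no figure of its own on this point, so there is none to reproduce.

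**Inputs from the SAP.** The window is 14 days, events are dated to window day 1, and status changes on the vaccination day.

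**Assumptions.** Vaccination day and onset day are uniform within the window. The infection rate is constant. Mean time before the first other vaccine, T, is 30, 60 or 120 days. Day 1 of a window counts as vaccinated if the vaccine is given that day.

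**Step 1: which infections move.** There are 14 × 14 = 196 pairs of vaccination day and onset day. Onset falls strictly after vaccination in 91 of them (46%). The 13 pairs with vaccination on day 1 are classified correctly. The other 78 of 91 (86%) are counted under the earlier status.

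**Step 2: how many days of events.** For vaccination on day v, 14 − v later days remain in the window. Summing over v = 2 to 14 gives 12 + 11 + … + 0 = 78, and 78/14 = 5.57 days per status change.

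**Step 3: effect on the *before* count and hazard ratio.**

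- Inflation of the count = 5.57/T.
- Misplaced share of the *before* row = 5.57/(T + 5.57).
- Diluted hazard ratio = (T × HR before + 5.57 × HR after)/(T + 5.57).

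| T (days) | Count inflation | Misplaced share | HR shown if true values are 1.00 before, 0.75 after | HR shown if true values are 0.75 before, 1.00 after |
|---|---|---|---|---|
| 30 | 18.6% | 15.7% | 0.961 | 0.789 |
| 60 | 9.3% | 8.5% | 0.979 | 0.771 |
| 120 | 4.6% | 4.4% | 0.989 | 0.761 |

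For example, at T = 30: (30 × 1.00 + 5.57 × 0.75)/35.57 = 34.18/35.57 = 0.961.

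**Step 4: check by simulation.** The settings were 400,000 participants, 1.5 infections per person-year, and vaccination times spread uniformly around means of 30, 60, 90 and 120 days in continuous time. True hazard ratios were 0.75 before and 1.00 after. Dating at true onset gave *before* hazard ratios of 0.75 to 0.76. Dating at the window start gave 0.80, 0.77, 0.77 and 0.77. The *after* hazard ratio stayed at about 1.00 under both rules.

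**Step 5: number of events.** At an assumed 0.5 to 2 infections per person-year, and if all 1706 participants had one status change during follow-up, 1706 × rate × 5.57/365 gives about 13 to 52 events.

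**The case against.** The strongest reply is that the Cox hazard ratio is less exposed than it looks. A reader might infer that events and risk time are assigned by different rules and that the hazard ratios are invalid for that reason. The SAP does not support this. A Cox model uses risk sets only at event times. If windows start at inclusion, every event falls on a window start, and cases and non-cases are both classified by their status that day. Part B, section 10.0, states that survey periods start from day 0. Part A says only that questionnaires are biweekly, so for Part A this is an assumption. On that assumption the risk-time mismatch affects counts and rates, not the hazard ratio. What remains is the dilution from misdated events.

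Other stronger readings also fail:

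- Not every post-vaccination infection in the window moves to *before*. Vaccination on day 1 is safe if that day counts as vaccinated. At a second status change the event moves to the earlier vaccine category.
- The dating rule is written only for self-reported respiratory infection. The GP or on-call component of the primary outcome also comes from a 14-day yes/no question, but the SAP gives it no event date, so the point cannot be extended to it as fact.
- The enrolment of 1239 participants between September 2020 and January 2021 makes short *before* times possible but does not establish them.

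The objection on size stands as well. Take 1239 participants, 0.5 to 2 infections per person-year and SE(log HR) ≈ 2/√events. At T = 30 there are 1239 × 35.57/365 × rate = 60 to 242 events, so the SE is 0.257 to 0.129. The shift of ln(0.961) = −0.040 is then 0.16 to 0.31 standard errors. At T = 60 it is 0.11 to 0.23. The illustration also assumes that the interaction appears in full on the day of vaccination. A slower onset would make the dilution smaller.

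None of this removes the misclassification or its one-way direction.

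**Conclusion.** The point holds in a narrow form, and its severity is minor. Followed as written, the plan counts some post-vaccination respiratory infections under the earlier vaccination status and modestly dilutes the before/after contrast. The dating follows from the SAP text alone. The size rests on assumed vaccination timing, infection rate and hazard ratios.

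A reader might infer that the rule could produce a false BCG effect or undermine the main results. It does neither. The rule applies equally in both arms, the unsplit analysis of this outcome is unaffected, and register outcomes are not dated this way.

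**What to change.** In section 7.0, Supplementary analyses, item 1, add for self-reported respiratory infection only:

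- Vaccination status is defined per questionnaire window, as the status on the window's first day, with a statement of how a vaccine given on that day is classified.
- Windows containing a status-changing vaccination date are left out, both events and risk time, so that status is constant in every analysed window.
- The version that keeps those windows, with status as of the window start, is reported as a sensitivity check.

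Register outcomes keep their exact dates.

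The cost is a few lines of SAP text and one data step. Up to 14 days of follow-up are lost per status change, in this supplementary analysis only. There is one downside to state openly: leaving out windows because of a vaccination later in the same window is mildly selective if illness delays vaccination, since the dropped windows would then tend to be free of events. The sensitivity version does not look ahead in this way, so agreement between the two would be reassuring.
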